6.1 Sample Size Estimation

This Phase IIA study is not formally powered.

6.1.1 Part 1

For Part 1, the proposed design of up to 6 patients per dose level has been selected to provide an assessment of the safety, tolerability and efficacy of up to 3 dose levels of ASLAN003, in order to select the most appropriate dose for further exploration in Part 2.

6.1.2 Part 2

The sample size of 20 patients for Part 2 has been selected to provide further efficacy and tolerability data at the selected dose level from Part 1, prior to conducting larger randomized trials in AML.

6.1.3 Sample Size Re-estimation

There are no planned sample size re-estimations.

6.2 Adjustments for Covariates

There are no planned adjustments for covariates.

6.3 Handling of Dropouts or Missing Data

In general, missing data will remain missing and will not be included in analyses. Exceptions are described below.

- Missing Baseline Data

If a baseline (Day 1) value is not available and a screening value is available for the same parameter, then the last screening value will be used as baseline. This value will also be used for calculations of changes from baseline.

6.4 Monitoring and Interim Analyses

6.4.1 Monitoring

The study will be monitored to ensure that the study is conducted and documented properly according to the protocol, good clinical practice (GCP), and all applicable regulatory requirements.

6.4.2 Interim Analysis

There are no interim analyses planned during Part 1 or Part 2.

6.5 Multiple Testing Strategy

There are no formal statistical analyses thus no corrections are planned for multiple testing.

6.6 Examination of Subgroups

Due to the small sample size, no subgroup analyses will be performed.

6.7 Stratification Factors

There are no stratification factors in this study.

7. Methods of Analysis

7.1 Overall Complete Remission Rate

A binary variable will be created to indicate complete response status for each patient (complete responder [CR or CRi] or non-responder [partial remission {PR} or treatment failure]).

For Part 1, AML response data will be listed, and summarized showing frequency and proportion of the best response (CR, CRi, PR or treatment failure) and OCRR (complete responder or non-responder) dose level and overall.

For Part 2, AML response data will be listed, and summarized showing frequency and proportion of the best response and OCRR, along with corresponding two-sided 80% confidence intervals (CIs) based on the Clopper-Pearson exact method.

7.2 Relapse-Free Survival

RFS will be listed for both study parts. For Part 2 only, if there are sufficient events, RFS will be summarized by using the Kaplan-Meier estimates to present 25th, 50th (median), and 75th percentiles, as well as the number and percentage of events and censored observations.

7.3 Clinical Benefit Rate

For Part 1, AML response data will be listed, and summarized showing frequency and proportion of CBR by dose level and overall.

For Part 2, AML response data will be listed, and summarized showing frequency and proportion of CBR, along with corresponding two-sided 80% CIs based on the Clopper-Pearson exact method.

7.4 BM blasts

Waterfall plots of the % change from baseline in BM blasts at Day 29, and the best % change from baseline in BM blasts will be presented. These plots will present each patient's value as a separate bar, with the bars ordered from the largest increase to the largest decrease.

For Part 1, all dose levels will be included on the same plot, but different bar types will be used to distinguish the different dose levels.

7.5 Time to Response

TTR data will be listed only.

7.6 Time to CR

TTCR data will be listed only.

7.7 Assessment of Safety and Tolerability

7.7.1 Assessment of Safety

All safety data will be assessed for the safety population.

All AE data will be listed along with information regarding initial study dose, dose at onset, onset time, duration, severity, and relationship to study treatment.

Treatment emergent AEs (TEAEs) are defined as AEs with an onset date on or after the start of treatment. The following summaries will be produced for both study parts, by dose group and overall for Part 1, for all TEAEs:

- An overview table of the incidence of TEAEs, grade 3+ TEAEs, SAEs, TEAEs leading to treatment discontinuation and TEAEs leading to death. For each summary category, the results will be shown overall (regardless of causality), and for the incidence of causally related TEAEs. For example, the overall incidence of TEAEs will be presented, as well as the incidence of TEAEs classified as at least possibly related to ASLAN003 by the Investigator.
- Summary of TEAEs by SOC and PT: Both the number and percentage of patients in each category (patient-level summary) and the number of episodes (episode-level summary). This summary table will be repeated for TEAEs attributed as causally related to study treatment.
- Summary of TEAEs, sorted in descending order of frequency (i.e. most frequent event shown first) presented by dose group (Part 1 only) and overall. The order of frequency will be determined by the most frequent preferred term overall. For each event, the results will be presented for all CTC grades, and also split by grade 1-2, and grade 3+.
- Summary of TEAEs attributed as causally related to study treatment, sorted in descending order of frequency (i.e. most frequent event shown first) presented by dose group (Part 1 only) and overall. The order of frequency will be determined by the most frequent preferred term overall. For each event, the results will be presented for all CTC grades, and also split by grade 1-2, and grade 3+.

- Summary of CTC grade 3 and above TEAEs sorted in descending order of frequency (i.e. most frequent event shown first). The order of frequency will be determined by the most frequent preferred term overall. Results will be presented by dose group (Part 1) and overall.
- A summary of CTC grade 3 and above TEAEs attributed as causally related to study treatment sorted in descending order of frequency (i.e. most frequent event shown first). The order of frequency will be determined by the most frequent preferred term overall. Results will be presented by dose group (Part 1) and overall.
- Summary of serious adverse events (SAEs) by PT.
- Summary of SAEs attributed as causally related to study treatment, sorted by PT.

Additionally, the following will be listed:

- AEs with outcome of death along with the date of onset, study day, initial study dose, dose at onset, treatment status at onset (pre-treatment, ongoing or post-treatment) and investigator's assessment of severity and relationship to study drug.
- All SAEs along with the date of onset, study day, initial study dose, dose at onset, treatment status at onset (pre-treatment, ongoing or post-treatment), date of resolution (if AE is resolved), investigator's assessment of severity and relationship to study drug.
- AEs leading to discontinuation of study drug, listed along with the date of onset, study day, initial study dose, dose at onset, treatment status at onset (pre-treatment, ongoing or post-treatment) and investigator's assessment of severity and relationship to study drug.

An AE will be considered to be causality related if a causality assessment of possibly, probably or definitely related is assigned by the Investigator.

If an AE is reported more than once during the study period the greatest severity and the worst-case attribution will be presented in summary tables. Any AEs commencing >28 days after discontinuation of study drug will not be included in the tabulations of AE data.

All clinical laboratory data (clinical chemistry, hematology and urinalysis data), vital signs and ECG data will be listed. In addition, all data measured on a continuous scale (except respiration rate and pulse) will be displayed graphically as described below:

- Patient profile plots over time including reference lines at the lower limit of normal (LLN) and upper limit of normal (ULN) where applicable for laboratory, vital signs and ECG data. For Part 1, separate plots will be produced for each cohort.
- For all continuous data except the haematological parameters, patient profile plots of the percentage change from baseline will be produced, including a reference line at zero. For Part 1, separate plots will be produced for each cohort.
- For all continuous data except the haematological parameters, box plots of the change from baseline over time, by dose group (Part 1), including a horizontal reference line at zero
- For haematological parameters, box plots of the absolute values over time, by dose group (Part 1), including a horizontal reference line at zero

To enable assessment of the potential for drug-induced liver injury, for all study parts the following outputs will be produced:

- A scatter plot of maximum on-treatment alanine aminotransferase (ALT) versus maximum on-treatment total bilirubin (x-axis), both expressed as multiples of the ULN, including reference lines at $3 \times \text{ULN}$ for ALT, and $2 \times \text{ULN}$ for total bilirubin. For each patient, the maximum ALT and maximum total bilirubin may occur at different visits
- A scatter plot of maximum on-treatment aspartate aminotransferase (AST) versus maximum on-treatment total bilirubin (x-axis), both expressed as multiples of the ULN, including reference lines at $3 \times \text{ULN}$ for AST, and $2 \times \text{ULN}$ for total bilirubin. For each patient, the maximum AST and maximum total bilirubin may occur at different visits.

In the event that the scatter plots of ALT or AST against bilirubin identify any potential Hy's law cases (patients with either both $\text{ALT} > 3 \times \text{ULN}$ and total bilirubin $> 2 \times \text{ULN}$, or both $\text{AST} > 3 \times \text{ULN}$ and total bilirubin $> 2 \times \text{ULN}$), profile plots over time will be produced for these patient's liver function tests (ALT, AST, ALP and total bilirubin), expressed in multiples of the ULN, showing all four FLT parameters on the same plot.

Physical examination data will be listed.

To further assess the tolerability of ASLAN003, dose intensity and treatment exposure, as defined in Section 3.2.2, will be listed and summarized by treatment arm. Dose intensity and exposure summaries will be presented by cycle for the first 3 cycles, and overall.

Swimmer plots of the time on treatment will be presented for all patients in the EFR set. The bars on these plots will be ordered as follows:

CR patients at the top, CRi patients next, PR next, non-responders next and NE patients at the bottom. Within each category they will be sorted from longest treatment duration to shortest treatment duration. Patients whose time on treatment is censored will be indicated. For responding patients, the start and end (actual or censored) time for response will also be indicated.

This plot will be repeated to account for dose modifications and interruptions.

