Treatment Cycles (28 days per cycle)	Day -28 to 0	Day 1	Day 8	Day 10	Day 15	Day 22	Day 1	Day 1	EOT	28 days after last administration of study medication	Every 12 weeks post EOT for RFS
Study Days		Day 1	Day 8	Day 10	Day 15	Day 22	Day 1	Day 1			
Study Allowed Window	NA	NA	±1	+1	±2	±2	±2	±2	Within 7 days of last dose of study treatment	±7	±7
Adverse Events/Serious Adverse Events ^a	X	X	X		X	X	X	X	X	X	
Prior and Concomitant Medication	X	X	X		X	X	X	X	X	X	
Laboratory Assessments											
Serum / urine β-human Chorionic Gonadotropin ^b	X								X		
Hematology	X	X	X		X	X	X	X	X		
Clinical Chemistry, Urinalysis ^c	X	X	X	X ^d	X	X	X	X	X		
Serology ^e	X										
Coagulation ^f	X				X				X		
Blood Pharmacokinetics Sampling ^g		X	X								
Bone Marrow Aspiration ^h	X						X	X			

Study Visit	Screening	Study Treatment Period							End of Treatment	Safety Follow-up	Survival Follow-Up
Treatment Cycles (28 days per cycle)	Day -28 to 0	Cycle 1					Cycle 2	Subsequent Cycles	EOT	28 days after last administration of study medication	Every 12 weeks post EOT for RFS
Study Days		Day 1	Day 8	Day 10	Day 15	Day 22	Day 1	Day 1			
Study Allowed Window	NA	NA	±1	+1	±2	±2	±2	±2	Within 7 days of last dose of study treatment	±7	±7
Other Assessment											
Survival status contact by phone ⁱ											X
Study Drug Administration											
ASLAN003		X	X	X	X	X	X	X			

Abbreviations: ALT = alanine aminotransferase; AST = Aspartate aminotransferase; CR = complete remission; CRi = complete remission with incomplete hematologic recovery; DNA = deoxyribonucleic acid; eCRF = electronic case report form; EOT = end of treatment; HBsAg = hepatitis B surface antigen; HBV = hepatitis B virus; NA = not applicable; PK=pharmacokinetics; RFS = relapse free survival.

Footnotes:

- a. Adverse event collection starts at the time of informed consent and continues until 28 days after the last administration of study drug. If a patient never receives study drug, but experience AE after informed consent form is signed, ONLY events the Investigator assessed as may have been caused by a study specific protocol procedure will be reported in eCRF.
- b. Serum or urine pregnancy test to be performed at the Screening visit for all females except those surgically sterile or 2 years postmenopausal. Serum or urine pregnancy tests will be performed at EOT. Unscheduled serum or urine pregnancy tests are allowed at the Investigator’s discretion.

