3.4 Duration of the study participation

The study duration consists of the following periods:

Screening Period: 28 days

Treatment Period: All patients will receive a continuous 28-day treatment cycle of ASLAN003 until disease relapse, treatment failure (defined as failure to achieve a PR or higher within 4 cycles) unacceptable toxicity, withdrawal of consent or death.

Follow-up Period: All patients will be required to complete a safety follow-up visit within 28 days after the last dose of study treatment. All patients achieving CR or CRi will be followed for survival every 12 weeks post end of treatment (EOT) until disease relapse or death (in the absence of disease relapse) to find out the RFS.

Visit Schedule: In order to address the primary objectives of the study, if treatment is interrupted for any reason, it is important that all planned safety and efficacy assessments are performed at the scheduled time, regardless of whether the patient is receiving study treatment, or not, at the time.

The planned duration of entire study (treatment and follow-up) is approximately 2 years.

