6.3.1.2 Definitions

An AE is any untoward medical occurrence that occurs in a patient or clinical investigation patient administered a pharmaceutical product, and which does not necessarily have to have a causal relationship with this treatment. An AE can therefore be any unfavorable and unintended sign (including abnormal laboratory finding), symptom, or disease temporally associated with the use of an investigational product, whether or not considered related to the product.

Fluctuations in the pre-existing conditions that do not represent a clinically significant exacerbation or worsening will not be considered AEs. Surgical procedures, planned before enrolment of the patient in the study, will not be considered AEs if the condition(s) was (were) known before study inclusion. In the latter case, the medical condition should be reported in the patient's medical history.

Progression of the malignancy or target disease under the study is generally not considered as an AE.

All AEs, including inter-current illnesses, occurring during the study will be documented in the eCRF. Concomitant illnesses, which existed before entry into the study, will not be considered AEs unless they worsen during the treatment period. All AEs, regardless of the source of identification (e.g., physical examination, laboratory assessment, ECG, reported by patient), must be documented.

Pre-existing conditions will be recorded in the eCRF system on the Medical History or appropriate page.

A treatment-emergent AE (TEAE) will be defined as an AE that begins or that worsens in severity after at least 1 dose of study drug has been administered.

When recording an AE, the Investigator should use the overall diagnosis or syndrome using standard medical terminology, rather than recording individual symptoms or signs. The eCRF and source documents should be consistent. Any discrepancies between the patient's own words on his/her own records (e.g., diary card) and the corresponding medical terminology should be clarified in the source documentation.

Details for completion of the AE case report form (CRF) (including judgment of relationship to study drug) are described in the CRF completion guidelines.

6.3.1.3 *Assessment of Adverse Events*

Each AE will be assessed by the Investigator with regard to the following categories.

6.3.1.4 *Seriousness*

A serious adverse event (SAE) is defined as any untoward medical occurrence that at any dose:

- Results in death;

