6.3.1.5 Intensity

Investigators should assess the severity of AEs according to CTCAE v4.03. In general, CTCAE v4.03 Severity Grades are:

- Grade 1: Mild; asymptomatic or mild symptoms; clinical or diagnostic observations only; intervention not indicated;
- Grade 2: Moderate; minimal, local or noninvasive intervention indicated; limiting age-appropriate instrumental Activities of Daily Living (ADL) (Instrumental ADL refer to preparing meals, shopping for groceries or clothes, using the telephone, managing money, etc.);
- Grade 3: Severe or medically significant but not immediately life-threatening; hospitalization or prolongation of hospitalization indicated; disabling; limiting self-care ADL (Self-care ADL refer to bathing, dressing and undressing, feeding self, using the toilet, taking medications, and not bedridden.);
- Grade 4: Life-threatening consequences; urgent intervention indicated;
- Grade 5: Death related to AE.

All changes in severity must be recorded in the eCRF.

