6.3.1.7 Recording Adverse Events

All AEs will be evaluated according to CTCAE version 4.03 and will be captured from the time of informed consent and continue until the safety follow-up assessment (28 days post-last dose of study drug). For the purpose of this study, fluctuations in the pre-existing conditions that do not represent a clinically significant exacerbation or worsening are not to be considered as AEs.

Prior to receiving study drug, only AEs that were assessed as related to study procedures will be recorded and reported. If a patient begins a new anti-leukemia therapy within 28 days after the last administration of study drug, the AE reporting period for non-serious AEs ends at the time the new therapy is started.

All AEs, as per the definition stated in the protocol regardless of the relationship to study drug, will be recorded in the eCRF.

All AE reports should contain a brief description of the event, date and time of onset, date and time of resolution, intensity, treatment required, relationship to study drug, action taken with the study drug (e.g. dose not changed, dose reduced, drug interrupt,, not applicable, and whether or not the AE led to the drug withdrawal), outcome (e.g. not recovered/resolved, recovering/resolving, recovered/resolved, recovered/resolved with sequelae, fatal, or unknown), and whether the event is classified as serious.

6.3.1.8 *Reporting Serious Adverse Events*

All SAEs will be recorded from signing of informed consent until 28 days after the last dose of the study drug. Prior to receiving investigational product, only SAEs that were assessed as related to study procedures will be reported.

If a patient begins a new anti-leukemia therapy within 28 days after the last administration of study drug, the SAE reporting period for SAEs ends at the time the new therapy is started.

The Investigator must report any SAEs, as per the definition stated in the protocol on the SAE page of the eCRF within 24 hours of becoming aware of the event. During eCRF inaccessibility, a paper SAE Form should be sent to the Sponsor's assigned safety representative (PAREXEL) by email within 24 hours of becoming aware of the event.

Email: [contact]

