8.4.3.1 Adverse Events

All AE data will be listed along with information regarding patient's original dose cohort, the dose at onset of the AE, onset time (study day), duration, severity, and relationship to study treatment.

Treatment emergent AEs (TEAEs) are defined as AEs with an onset date on or after the start of study treatment. The following summaries will be produced for all TEAEs.

- An overview table of the incidence of TEAEs, Grade 3+ TEAEs, SAEs, TEAEs leading to treatment discontinuation and TEAEs leading to death, by dose cohort (Part 1 ONLY) and overall. For each summary category, the results will be shown overall (regardless of causality), and for the incidence of causally-related TEAEs. For example, the overall incidence of TEAEs will be presented, as well as the incidence of TEAEs classified as at least "possibly related" to ASLAN003 by the Investigator;
- Summary of TEAEs by system organ class (SOC) and preferred term: Both the number and percentage of patients in each category (patient-level summary) and the number of episodes (episode-level summary). This summary table will be repeated for TEAEs attributed as causally related to study treatment;

- Summary of TEAEs occurring in patients, sorted in descending order of frequency (i.e., most frequent event shown first) presented by dose cohort (Part 1 ONLY) and overall. The order of frequency will be determined by the most frequent preferred term overall. For each event, the results will be presented for all CTCAE grades, and also split by Grade 1-2, and Grade 3+;
- Summary of TEAEs attributed as causally related to study treatment, and occurring in patients, sorted in descending order of frequency (i.e., most frequent event shown first) overall. Results will be presented by dose cohort (Part 1 ONLY) and overall. For each event, the results will be presented for all CTCAE grades, and also split by Grade 1 to Grade 2, and Grade 3+;
- Summary of CTCAE Grade 3 and above TEAEs sorted in descending order of frequency (i.e., most frequent event shown first). The order of frequency will be determined by the most frequent preferred term overall. Results will be presented by dose cohort (Part 1 ONLY) and overall;

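### The TEAE tables are defined by onset date alone, so an adverse event recorded before dosing that worsens on drug is left out, although protocol 6.3.1.2 counts it

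*SAP*

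**What the plan says.** Three sections define the same term.

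- Protocol 6.3.1.2 (Definitions): a TEAE is "an AE that begins or that worsens in severity after at least 1 dose of study drug has been administered".
- Protocol 8.4.3.1 (Adverse Events, statistical methods): "Treatment emergent AEs (TEAEs) are defined as AEs with an onset date on or after the start of study treatment".
- SAP 7.7.1 (Assessment of Safety): "Treatment emergent AEs (TEAEs) are defined as AEs with an onset date on or after the start of treatment".

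The summaries listed in SAP 7.7.1 are stated to be for all TEAEs. They include the overview table, the SOC and preferred-term tables, the Grade 3+ tables and the causally related versions.

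Other sections decide how far the difference matters.

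- Protocol Table 1, footnote a: "Adverse event collection starts at the time of informed consent and continues until 28 days after the last administration of study drug". The same footnote limits reporting to procedure-related events, but only for patients who never receive study drug.
- Protocol 6.3.1.7: "Prior to receiving study drug, only AEs that were assessed as related to study procedures will be recorded and reported". This limit is not confined to never-dosed patients.
- Protocol 3.4: "Screening Period: 28 days".
- Protocol 6.3.1.5: "All changes in severity must be recorded in the eCRF".
- Protocol 6.3.1.2 also sends pre-existing conditions to the medical history page. An illness present before entry becomes an AE only if it worsens during treatment. The section does not say which start date that AE should carry.

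**The concern.** Two definitions of one safety term cannot both be programmed, and the SAP's is the narrower. It omits the case where an event already on record before the first dose becomes more severe on drug, which 6.3.1.2 expressly includes. Safety and tolerability is a co-primary endpoint in Part 1 and one of the bases for choosing the Part 2 dose. With six patients per cohort, a single patient missing from a row can be visible in the incidence by dose. The documents foresee events that start before treatment and still matter later: both statistical sections list SAEs, fatal AEs and AEs leading to discontinuation by whether onset came before, during or after treatment. Under the onset-only rule, an event that began in screening, worsened on drug and led to stopping would appear in the listing but not in the overview row for TEAEs leading to discontinuation.

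**Working it through.** The plan states no figure on this point, so there is none to reproduce. The check compares definitions and then bounds the effect.

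**Step 1: compare the sets.** Let A be the events with onset on or after the first dose. Let W be the events with a recorded pre-dose onset whose grade rises after the first dose. Events dated on the day of the first dose are taken as post-dose under both rules.

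- Protocol 6.3.1.2 counts A together with W.
- Protocol 8.4.3.1 and SAP 7.7.1 count A only.

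A is contained in the union of A and W, so every count under the SAP is equal to or lower than the count under 6.3.1.2. The two agree when W is empty.

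**Step 2: look for a rule that moves W into A.**

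- Protocol 6.3.1.5 requires severity changes to be recorded, but does not require a new record or a new onset date.
- Protocol 6.3.1.2 turns a worsened pre-existing illness into an AE without assigning its date.
- SAP 7.7.1 shows the greatest severity and worst attribution for an AE reported more than once. That selects the grade and attribution displayed; it does not make an event with pre-dose onset treatment-emergent.

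None of these closes the gap. A site that enters the worsening as a fresh event would close it in practice, but the documents neither require nor forbid that.

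**Step 3: ask how large W can be.**

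- If protocol 6.3.1.7 is followed, recorded pre-dose AEs are procedure-related only. W is then the subset of those, arising in a window of up to 28 days, that later rise in grade.
- If footnote a is read as limiting only never-dosed patients, W can include any AE arising between consent and first dose in a treated patient.
- Worsened pre-existing conditions fall into W only if the site enters the original start date instead of the date of worsening.

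The documents give no count for any of these, so the size of W is unknown.

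**Step 4: bound the effect on a table row.** If k patients are missing from a row of n patients, the row falls by at most 100 × k/n percentage points. The bound is reached only if none of the k patients has another event qualifying for that row. The values of k are assumptions for illustration; n comes from protocol 8.2 and the synopsis.

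| Row denominator | k = 0 | k = 1 | k = 2 |
|---|---|---|---|
| Part 1 cohort, n = 6 | 0 | 1/6 = 16.7 | 2/6 = 33.3 |
| Part 1 overall, n = 18 | 0 | 1/18 = 5.6 | 2/18 = 11.1 |
| Part 1 overall, n = 24 | 0 | 1/24 = 4.2 | 2/24 = 8.3 |
| Part 2, n = 20 | 0 | 1/20 = 5.0 | 2/20 = 10.0 |

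For broad rows, such as any TEAE, one other qualifying event in the same patient leaves the figure unchanged. The bound is more likely to be reached in single preferred-term rows.

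**The case against.** The strongest reply is that little is lost. Protocol 6.3.1.7 keeps most pre-dose events out of the AE record. A condition present at entry belongs in medical history and becomes an AE only through worsening on treatment, so the natural onset date is the date of worsening and the onset-only rule captures it. All AEs are listed whatever their onset. Laboratory and ECG data have their own listings and plots, and the plots of maximum on-treatment ALT and AST against bilirubin do not depend on the TEAE flag. The steering committee reviews all clinical information, not a TEAE rate threshold, and its power to halt recruitment (protocol 6.3.1.6, Note 2) turns on probably or definitely related reactions in the first cycle.

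Most of this stands, and it limits the size of the problem. It also answers a stronger reading that a reader might infer: that cytopenias, infections or fatigue present at entry and worsening on drug drop out of the tables as a matter of course, so that Grade 3+ and related rates are biased downward. The documents do not support that. They make such worsening an AE and leave its date open; nothing says it keeps an early onset.

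What the reply does not remove is the contradiction. The dating it relies on is a sensible convention that neither document states, and the limit on pre-dose events is worded differently in 6.3.1.7 and in footnote a.

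**Conclusion.** The inconsistency is certain: protocol 6.3.1.2 includes worsening, while protocol 8.4.3.1 and SAP 7.7.1 do not, and nothing reconciles them. The direction is also settled: TEAE, Grade 3+, related and discontinuation counts under the SAP are equal to or lower than under 6.3.1.2. The size is not known. It may be small or zero, and it depends on which pre-dose events sites record and on how they date a worsened condition. The figures of 16.7 points (one of 6) and 5 points (one of 20) are ceilings for one patient in one row, not an expected loss per affected patient. This is a definitional error worth correcting because safety is co-primary in Part 1, the cohorts are small and the correction is cheap. It is not evidence that the planned safety review would miss a toxicity signal.

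**What to change.** Use one definition, that of protocol 6.3.1.2, in SAP 7.7.1 and protocol 8.4.3.1: an AE is treatment-emergent if its onset is on or after the first dose, or if its CTCAE grade increases after the first dose. Add that a worsened event, including a worsened pre-existing condition, is dated for analysis at its first post-dose grade increase, and that the tables show the worst post-dose grade. In the same edit, state which pre-dose AEs are recorded for patients who go on to be dosed, since protocol 6.3.1.7 and Table 1 footnote a differ.

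The cost is a few sentences across the two documents and a small derivation from severity changes that protocol 6.3.1.5 already requires to be recorded. Reported TEAE rates may rise slightly.
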